4.2.8 Pharmacokinetics analysis

Ceftaroline plasma concentration data, along with other information including demographic data, will be combined with appropriate data from other clinical studies and analyzed using a population PK approach and reported separately.

PK schedule assignment data, sample collection data and plasma concentration data will be listed by age cohort and patient for the PK Analysis Set.

5. APPENDICES

APPENDIX A	Non-eligible pathogens
APPENDIX B	Criteria for potentially clinically significant laboratory results
APPENDIX C	Adverse Events of Special Interest

Appendix A

Non-eligible pathogens

Table 2 Pathogen Classifications for Study

Always	Never	Sometimes
Enterobacteriaceae	ESBL phenotype positive Enterobacteriaceae	Enterococcus spp.*
Staphylococcus aureus	Other Enterobacteriaceae not susceptible to study drug received	
Streptococcus spp.	Other non- Enterobacteriaceae Gram negative bacteria	
Coagulase-negative staphylococci		
Streptococcus spp. (except viridans Streptococci)	Non-fermentative Gram-negative bacteria including Pseudomonas spp. viridans Streptococci	
	Anaerobes	
	Fungal pathogens (including yeast)	
	Parasitic pathogens	
	Viral pathogens	

Table 1 represents the latest known list for pathogens susceptible to ceftaroline. If more data become available during the course of this study, then this list will be updated appropriately.

* Based on investigator determination.

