8.4.2. Microbiological response definitions

8.4.2.1. Microbiological Outcome at Test-of-Cure

The per-pathogen microbiological outcome categories at EOT and TOC are defined in [Table 6](#). Favourable microbiological outcomes are eradication or presumed eradication. Per-patient microbiological response at EOT and TOC will be determined programmatically based on individual outcomes for each baseline pathogen. In order for a patient to have a favourable microbiological response, the outcome for each baseline pathogen must be favourable (eradicated or presumed eradicated). If the outcome for any pathogen is unfavourable (persistence or presumed persistence), the patient will be considered to have an unfavourable microbiological response.

Baseline pathogens will be determined based on central laboratory data. Rules for determination of pathogens will be described in the SAP.

Table 6 Per-pathogen microbiological outcomes categories at End of Treatment and Test-of-Cure

Microbiological Response ^a	Definition
Eradication	Source specimen demonstrated absence of the original baseline pathogen
Presumed eradication	Source specimen was not available to culture and the patient was assessed as a clinical cure
Persistence	Source specimen demonstrates continued presence of the original baseline pathogen
Presumed persistence	Source specimen was not available to culture and the patient was assessed as a clinical failure
Indeterminate	Source specimen was not available to culture and the patient's clinical outcome was assessed as indeterminate

a For patients who are clinical failures before TOC, the microbiological outcome will be carried forward to TOC and will be determined based on the cultures and/or clinical outcome at the time of the early clinical failure determination.

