23 August 2016	V2.2 Updated to incorporate client review comments on V2.1: In section 3.1.1.1, if the intensity of an Adverse Event (AE) is missing, the AE will be regarded as having missing rather than severe intensity; If the relationship of an AE to IMP is missing, the AE will be regarded as having a missing relationship to IMP rather than being related to IMP; and an additional table for the duration of prior medication was added. Updated to incorporate protocol amendment 3 changes: inclusion criteria 3, 4 and 5 were revised so that patients must meet at least 1 of the listed laboratory criteria, rather than 2 of the criteria and justification provided for the dose increase to 6mg/kg in the previous protocol amendment.
5 September 2016	V2.3 Additional details added to the amendment history for V2.2 of the SAP. The text of SAP Appendix A was clarified. Listing was replaced with Appendix in the “Source: ...” footnote of Tables. Listing xx.x.xx was removed from the footnotes of the TFL appendix shells, as not required.
6 December 2017	V2.4 Updated to incorporate protocol amendment 4. Version of protocol and CRF updated. Additional Tables and Listings added further to receipt of Pfizer review comments. Unnecessary appendices removed and cross-references within the SAP updated. Details in relation to the DSMB modified and DSMB Tables and Listings removed as no further DSMBs to occur.
12 January 2018	V2.5 Updated to incorporate final Pfizer review comments on V2.4 SAP and TFL shells. Additional Tables and Listings added. Further TFL numbering changes incorporated. Additional Microbiological ITT population added. Further clarification of non-eligible organisms provided in Appendix A.
16 March 2018	V2.6 Incorporate final changes to the SAP ahead of database lock. Update to include list of AESIs. Update to Micro-ITT population definition. Post Data Review Meeting changes incorporated.

Date	Brief description of change
22 March 2018	V2.7 Appendix A updated to move Enterococcus species from never to sometimes a pathogen based on investigator determination.

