2.1.4 Microbiological Intent-to-Treat Analysis Set

The Microbiological Intent-to-treat (Micro-ITT) Analysis Set will include all ITT subjects who have one or more potentially causative baseline pathogens identified.

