3.2.1.2 Per-pathogen and per-patient microbiological response variables at EOT and TOC

The per-pathogen microbiological outcome categories for pathogens identified at baseline are defined in [Table 7](#). Local microbiology data will only be used when central data is not available, for example, samples were not sent to the central laboratory for processing. Please see [section 3.3.1.3](#) for further details.

Table 7 Per-pathogen microbiological response categories

Microbiological Response ^a	Definition	Response Category
Eradication	Source specimen demonstrated absence of the original baseline pathogen	Favorable
Presumed eradication	Source specimen was not available to culture and the patient was assessed as a clinical cure	Favorable
Persistence	Source specimen demonstrates continued presence of the original baseline pathogen	Unfavorable
Presumed persistence	Source specimen was not available to culture and the patient was assessed as a clinical failure	Unfavorable
Indeterminate	Source specimen was not available to culture and the patient's clinical outcome was assessed as indeterminate	Indeterminate

^a For patients who were clinical failures before TOC, the microbiological outcome will be carried forward to TOC and will be determined based on the cultures and/or clinical outcome at the time of the early clinical failure determination.

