3.3.1.3 Baseline microbiological assessment variables for blood, CSF, urine, and other specimens

Identification of pathogens and susceptibility results will be recorded by both the local microbiology laboratory and the central reference laboratory. The identification and susceptibility results of the central microbiology reference laboratory will be regarded as definitive, if after re-testing, any discrepancies noted are not resolved. In the circumstance that the central lab could not isolate any organism from the submitted specimen, the local lab result will be used for organism identification (not including a result of "No Growth" at the central laboratory, which should be reported).

Microbiological assessments at baseline include collection data, culture data, antibiotic susceptibility data, and gram stain data:

- Collection data: specimen collected yes/no, type of specimen, reason for no specimen, specify if attempt made but unable to obtain, collection date and time and specimen acquisition method

- Culture data: specimen work up performed by, culture outcome, culture source location, laboratory name and identifier, pathogen type, isolate identification, isolate classification, isolate quantitation for 1 µL, 5 µL, 10 µL plates (for urine specimens only), isolate sent to central lab yes/no, reason if no specimen sent to central laboratory, accession identifier primary and secondary
- Antibiotic susceptibility data: local susceptibility tested yes/no, isolate identification, antibiotics tested, susceptibility, susceptibility criteria and susceptibility method
- Gram stain data: gram stain done yes/no, specify if no gram stain done and gram stain results, for example, epithelial cell results, etc.

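### SAP Appendix A counts coagulase-negative staphylococci as a pathogen without any condition, so a recovering infant whose only isolate may be a contaminant scores as a favourable microbiological response

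*SAP*

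**What the plan says.** Protocol section 8.4.2.1 hands the matter to the SAP: "Rules for determination of pathogens will be described in the SAP". The SAP answers in two places.

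- **Appendix A** sorts organisms into Always, Never and Sometimes. "Coagulase-negative staphylococci" stands under Always with no footnote or condition. Enterococcus is the only entry under Sometimes, and its footnote reads "Based on investigator determination".
- **Section 3.3.1.3** says when the central laboratory result overrides the local one. That settles which organism grew, not whether it was a contaminant. The same section records specimen type, culture source, isolate classification, and "collection date and time and specimen acquisition method", but no rule uses these items to judge an isolate.

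Section 2.1.4 defines the Micro-ITT set, which "will include all ITT subjects who have one or more potentially causative baseline pathogens identified". The term for causation in that definition is not explained. In Table 7 (section 3.2.1.2), presumed eradication is a favourable category, defined as "Source specimen was not available to culture and the patient was assessed as a clinical cure".

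**The concern.** A species-only rule suits organisms whose growth nearly always means infection. CoNS live on skin, so a lone positive culture may reflect how the specimen was taken. That is general microbiological knowledge and is not stated in the documents; I treat it as an assumption. The SAP already accepts for Enterococcus that species alone may not decide the matter, yet gives CoNS no comparable check.

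At stake is what three results mean: the Micro-ITT clinical cure rate, the microbiological favourable rate (MITT and Micro-ITT), and the CoNS entries in the by-pathogen tables. If some isolates did not cause the sepsis, recovery in those infants says nothing about activity against CoNS, yet it is tabulated as such. With 24 infants planned in three cohorts of 8, a few isolates can shift a cell visibly.

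**Working it through.** **The plan's own figure.** There is none to reproduce: no expected number of CoNS isolates, contamination rate or expected favourable rate. The only planned count is 24 = 3 × 8, and the point does not depend on it.

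**Tracing the rule for an infant whose only baseline isolate is CoNS**

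1. Entry (Protocol section 3.1): at least two clinical criteria, at least one laboratory criterion, and suspected or proven bacterial infection needing IV antibiotics. A proven organism is not required.
2. Appendix A: CoNS is Always a pathogen. The change log for SAP version 2.7 supports reading the columns this way: "Appendix A updated to move Enterococcus species from never to sometimes a pathogen based on investigator determination". I use the log only to interpret the column headings.
3. SAP section 2.1.4: one baseline pathogen is enough for Micro-ITT. Section 3.2.1.2 counts blood, urine, CSF and other specimens. No minimum number of cultures appears anywhere.
4. SAP section 3.2.1.2, for an infant who recovers: a negative culture at the visit gives eradication; no culture plus clinical cure gives presumed eradication. Both are favourable.

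**Size, by illustration only.** Let *x* of *n* infants with true pathogens be favourable. Add *c* infants with a contaminant, of whom a fraction *q* are favourable:

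rate = (*x* + *cq*) / (*n* + *c*)

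The rate rises if *q* > *x/n* and falls if *q* < *x/n*. The SAP's Jeffreys 95% limits are the 2.5% and 97.5% points of Beta(*f* + 0.5, *N* − *f* + 0.5), for *f* favourable out of *N*. All counts below are assumed.

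| Base | Added | Result | Jeffreys 95% CI |
|---|---|---|---|
| 4/6 | none | 66.7% | 28.6 to 92.3 |
| 4/6 | 1, recovers | 5/7 = 71.4% | 35.2 to 93.5 |
| 4/6 | 4, all recover | 8/10 = 80.0% | 49.7 to 95.6 |
| 4/6 | 4, two recover | 6/10 = 60.0% | 30.4 to 84.7 |
| 6/8 | none | 75.0% | 40.8 to 94.4 |
| 6/8 | 1, recovers | 7/9 = 77.8% | 45.6 to 95.1 |
| 6/8 | 4, all recover | 10/12 = 83.3% | 56.4 to 96.4 |
| 4/8 | none | 50.0% | 19.9 to 80.1 |
| 4/8 | 4, all recover | 8/12 = 66.7% | 38.8 to 87.5 |

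Across these cases, full recovery raises the rate by 2.8 points (75.0 to 77.8) to 16.7 points (50.0 to 66.7). Recovery of two in four lowers it by 6.7 points (66.7 to 60.0). From 6/8, an average recovery of 60% gives (6 + 4 × 0.6)/12 = 70.0%, a fall of 5.0 points.

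**What is not reached.** The safety analysis uses all infants given any ceftaroline fosamil, whatever they grew. MITT membership does not require a pathogen, so counting CoNS as one brings nobody into MITT and does not change how the overall MITT clinical cure is scored.

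**The case against.** The case on the other side has several good parts.

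- **The premise is external.** Neither document says that CoNS isolates are often contaminants, and an inclusive Always could be deliberate. This stands, and it is why Micro-ITT should be kept and supplemented, not replaced.
- **The rule is partly silence.** A reader might infer that Appendix A declares one culture of any specimen sufficient. It does not say so. That follows only because no limit is stated there or elsewhere. The Micro-ITT wording on possible causation could allow a filter, but no criterion is given, and Always leaves little room for one. The appendix is titled as a list of non-eligible organisms, and its footnote speaks of susceptibility to ceftaroline, so the sponsor should confirm what the columns mean.
- **These infants are ill.** Entry demands clinical and laboratory signs of sepsis. That makes infection likely; it does not make the CoNS isolate its cause.
- **Repeat cultures are expected.** Protocol section 5.2.1 asks that positive blood cultures be repeated until sterile, so presumed eradication is not the only route. The infant is still favourable by the other one.
- **The effect is not hidden.** A reader might infer that CoNS results are buried in the total. SAP sections 4.2.3, 4.2.7.1 and 4.2.7.2 provide summaries by organism and specimen, responses by pathogen, and patient listings. What is missing is a rule, set without knowledge of outcome, for separating supported from unsupported CoNS isolates.

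**Conclusion.** The point holds as a gap in the pathogen rules. CoNS is counted unconditionally, and a recovering infant with CoNS as the sole baseline isolate is scored favourable whether or not the organism caused the illness. This rests on reading Always as meaning that the organism counts as a pathogen, and on the assumption that some CoNS isolates may be contaminants.

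A reader might go further and infer that the plan inflates ceftaroline's microbiological response. The documents do not support that. They give neither a contamination rate nor recovery rates for the two groups, and the assumed counts produce shifts from −6.7 to +16.7 points with wide, overlapping intervals. Size and direction are both unknown.

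The reach is limited to secondary, descriptive results: Micro-ITT, the microbiological tables and the by-pathogen rows. There is no hypothesis test to distort. The change is worth making because it is cheap and settles how the CoNS results may be read.

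**What to change.** Keep Micro-ITT as defined. Before database lock, pre-specify two sensitivity rows for clinical and microbiological response:

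1. **Without CoNS-only infants:** leave out infants whose only baseline isolate is CoNS, and list them.
2. **Supported CoNS, where data allow:** keep CoNS only if evidence collected before the first dose supports it. This means the same CoNS in two or more cultures taken before that dose, or an investigator determination, as for Enterococcus, documented without reference to outcome.

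Post-dose cultures should not be used to confirm CoNS. A positive repeat at EOT or TOC is itself persistence, so such a rule would select infants by unfavourable outcome. The time limit matters because cultures are taken only when clinically indicated as part of regular care (Protocol section 4.1.1.3), and paired baseline cultures are not required.

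The cost is one derived flag and a few table rows; version 2.7 made a comparable edit to Appendix A for Enterococcus. The downside is that the rows will be small, may be nearly empty in some cohorts, and will leave out some true CoNS sepsis with a single positive culture. They should therefore stand beside Micro-ITT and not replace it.

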3.6. Methods for ensuring blinding

This study is not blinded. The investigators, pharmacists or designees, study centre personnel, and parent(s)/legally-acceptable representative(s) will be aware of study therapy being administered.

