4.1.1 Data quality

The clinical database will be cleaned prior to analysis; see PRA Clinical Informatics Plan for details. Beyond the data screening built into the PRA Clinical Informatics Plan, the PRA programming of analysis datasets, tables, figures, and listings (TFLs) will provide additional data screening.

Review of a pre-freeze TFL run on clean patients and a post-freeze TFL run on the frozen database will allow for further data screening prior to lock. The post-freeze TFL will be discussed with Pfizer in a data review meeting to identify any final data issues and seek corrections prior to database lock. The PRA statistician and Pfizer must approve database lock.

PRA's goal is to ensure that each TFL delivery is submitted to the highest level of quality. Our quality control procedures will be documented separately in the study-specific clinical programming quality control plan.

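### SAP Appendix A leaves Enterococcus's status as a baseline pathogen to the open-label investigator, with no criterion and no requirement that the decision predate the outcome

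*SAP*

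**What the plan says.** SAP Appendix A classes organisms in three columns. All but one entry sit in the always or never column. *Enterococcus* spp. stands alone under sometimes, with the footnote "Based on investigator determination". The appendix gives no criterion (specimen, quantity, sole isolate), no deadline and no second reader.

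The classification feeds the analysis as follows:

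- SAP 2.1.4 defines Micro-ITT as the ITT infants "who have one or more potentially causative baseline pathogens identified".
- SAP 4.2.7.1 and 4.2.7.2 tabulate clinical and microbiological response by baseline pathogen, and give Micro-ITT rates with 95% Jeffreys intervals.
- Protocol 8.4.2.1 bases baseline pathogens on central laboratory data and leaves the rules to the SAP.
- Protocol 3.6 states "This study is not blinded". Protocol 8.4.1.1 and 8.4.1.2 have the investigator rate clinical outcome at EOT and TOC.

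On dates, the SAP amendment history describes V2.6 (16 March 2018) with "Incorporate final changes to the SAP ahead of database lock" and "Post Data Review Meeting changes incorporated". V2.7 (22 March 2018) reads "Appendix A updated to move Enterococcus species from never to sometimes a pathogen based on investigator determination".

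**The concern.** One unblinded person decides whether an enterococcal isolate counts and also whether the infant was cured. If the first decision can follow the second, an Enterococcus-only infant can enter or stay out of Micro-ITT according to outcome.

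The two judgements are tied more closely by SAP 3.2.1.2. Where no follow-up culture exists, the microbiological outcome is presumed from the clinical one. Follow-up cultures are taken only when clinically indicated (Protocol 4.2.5.3 and 4.3.1.3), so presumed outcomes are likely to occur. The same investigator could then settle both an infant's place in the denominator and, by presumption, whether that infant counts as favourable.

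At stake are the Micro-ITT rates and the per-pathogen rows. A Jeffreys interval describes binomial sampling error and makes no allowance for membership chosen by outcome.

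**Working it through.** **Does the plan close the gap elsewhere?** The nearest text is SAP 3.3.1.3, which lists isolate classification among the baseline culture fields. That names a data item. It does not say who makes the classification, on what criterion, or that it is fixed before EOT. The same section makes the central laboratory definitive for identification and susceptibility, which is a different question from whether an isolate caused the infection. SAP 2.1.4 does not cite Appendix A, but Appendix A is the only place where the SAP says which organisms count as pathogens.

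**Which analyses are exposed?**

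- Micro-ITT membership: exposed for infants whose only isolate is Enterococcus.
- Per-pathogen tables: exposed, because the Enterococcus row depends on the determination.
- Mixed infections: the infant stays in Micro-ITT either way. The per-patient response could change only if the two organisms had different outcomes.
- MITT membership: unclear. SAP 2.1.3 excludes resistant pathogens by CLSI criteria, and the next sentence, on fungal, parasitic and viral causes, cites Appendix A.
- Safety Analysis Set and overall ITT clinical response: not exposed, since neither uses pathogen status.

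**Size.** The plan has no figure to reproduce: the sample size is 3 × 8 = 24 without a formula, and SAP 4.1 rules out hypothesis tests. Neither the Micro-ITT size nor the number of Enterococcus-only infants is given. I assume a base of 8 to 12 infants, that is 24/3 to 24/2, with 6/8 or 10/12 favourable.

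Adding one infant to a base of x favourable out of n changes both numerator and denominator:

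- if favourable, the shift is (x+1)/(n+1) − x/n = (n−x)/[n(n+1)];
- if not, the shift is x/(n+1) − x/n = −x/[n(n+1)].

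| Base (Jeffreys 95%) | One favourable added | One unfavourable added |
|---|---|---|
| 6/8 = 75.0% (40.8–94.4) | 7/9 = 77.8% (45.6–95.1), +2/72 = +2.8 points | 6/9 = 66.7% (34.8–89.6), −6/72 = −8.3 points |
| 10/12 = 83.3% (56.4–96.4) | 11/13 = 84.6% (59.1–96.7), +2/156 = +1.3 points | 10/13 = 76.9% (50.3–93.0), −10/156 = −6.4 points |

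**Illustration of the worst mechanism.** Suppose k Enterococcus-only infants were counted only when cured, with m other infants and a true rate p for all. The expected rate is the sum over j = 0 to k of Bin(j; k, p) × (mp + j)/(m + j). For m = 10, k = 2, p = 0.8:

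0.04 × 8/10 + 0.32 × 9/11 + 0.64 × 10/12 = 0.0320 + 0.2618 + 0.5333 = 0.827, or +2.7 points.

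Over m = 8 to 12, k = 1 to 3 and p = 0.6 to 0.9, the expected excess runs from +0.7 to +7.1 points. This shows what such a rule would do. It is not an estimate of what was done.

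**The case against.** The strongest reply is that this touches only supportive, descriptive output. Safety is the primary objective, the protocol's efficacy measure is clinical outcome in MITT, and Micro-ITT was added by the SAP at V2.5. Baseline cultures and microbiological responses are listed by patient for the ITT set (SAP 4.2.3 and 4.2.7.2), so a reader could recount about 24 infants by hand. All of that stands, and it limits the weight of the point. It does not supply the missing rule, and readers of the summary tables will not normally rebuild them from listings.

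A second reply is that the determination may have been a baseline CRF entry. It may have been; the documents do not settle it. If it was, requiring a date before EOT costs nothing.

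A third is that Appendix A allows for updating. That sentence concerns the list of ceftaroline-susceptible organisms as data accrue. It says nothing on how to judge causality.

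Four stronger readings are tempting and are not supported:

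- *That both late changes followed review of frozen-data tables.* SAP 4.1.1 plans that "The post-freeze TFL will be discussed with Pfizer in a data review meeting to identify any final data issues", but the log does not say what the V2.6 meeting saw. Equating the two is an inference. V2.6 also lists the Micro-ITT update separately from the post-meeting changes.
- *That the rule was changed after lock.* V2.6 precedes lock. For V2.7 the documents do not say.
- *That the rates are biased.* No determination is shown to have been made with the outcome known.
- *That each infant moves a rate by 1/n, or 8 to 13 points at n = 12 to 8.* That needs an outcome reversed within a fixed set, or every other infant having the opposite outcome. Adding an infant to the sets assumed here moves the rate by less.

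**Conclusion.** The point holds as a gap in a stated rule. For one genus, pathogen status rests on an unblinded judgement with no criterion and no time limit, made by the person who rates outcome. Micro-ITT membership for Enterococcus-only infants and the per-pathogen rows could therefore depend on outcome.

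Under assumed bases of 6/8 to 10/12 favourable, one such infant shifts the rate by about +1 to +3 points if favourable or −6 to −8 points if not, within intervals that are wide and overlap. The number of such infants is unknown and may be zero.

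The classification changed in V2.7, six days after a version that had already taken in changes from a data review meeting. That sequence calls for disclosure; it does not show that results drove the change. The point is worth correcting before the microbiological tables are reported, and it does not bear on the trial's primary conclusion.

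**What to change.** 1. Extend the Appendix A footnote by one sentence: Enterococcus counts as a baseline pathogen only where the investigator's determination was made from baseline information and is dated before the EOT assessment.
2. Report the Micro-ITT and per-pathogen results twice, with all enterococci counted and with none. Neither version can be selected by outcome, so a reader can see whether the determinations matter.
3. State in the report that the classification changed in V2.7, after the data review meeting, and whether that was before database lock.

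A rerun under the V2.5 Micro-ITT definition is not proposed, because that definition is not in the documents. Nor is a particular specimen rule, which nothing in the documents supports over another.

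Cost: one sentence in the SAP, one disclosure in the report and one repeat of a few descriptive tables. No new data are needed.
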